16	Publication Policy.....	33 3
17	Literature References.....	34 4
	Supplements/Appendices.....	36 6
	Appendix A: Schedule of Events (following Acquisition of Informed Consent).....	36 6

LIST OF ABBREVIATIONS

AE	Adverse Event/Adverse Experience
AESI	Adverse Event Special Interest
ALT	Alanine Aminotransferase
ANC	Absolute Neutrophil Count
AUC	Area Under the Curve
CFR	Code of Federal Regulations
CHRU	Child Health Research Unit
CL	Clearance
Cmax	Maximum serum concentration
CNS	Central Nervous System
CRF	Case Report Form
CSF	Cerebrospinal fluid
eCRF	Electronic Case Report Form
EU	European Union
FDA	Food and Drug Administration
FWA	Federalwide Assurance
GCP	Good Clinical Practice
HSV	Herpes Simplex Virus
ICH	International Conference on Harmonisation
IEC	Independent or Institutional Ethics Committee
IND	Investigational New Drug Application
IRB	Institutional Review Board
IV	Intravenous
KG	Kilogram
MG	Milligram
mL	Milliliter
NIH	National Institutes of Health
OHRP	Office for Human Research Protections
PCR	Polymerase Chain Reaction
PHI	Protected Health Information
PI	Principal Investigator
PK	Pharmacokinetics
SAE	Serious Adverse Event/Serious Adverse Experience
SEM	Skin, Eye, and Mouth Disease
Vd	Volume of distribution
US	United States
WBC	White Blood Cell Count

PROTOCOL SUMMARY

Title:	Evaluation of the Pharmacokinetics and Pharmacodynamics of Valacyclovir in Neonates with neonatal HSV disease who have completed standard of care treatment with acyclovir
Phase:	IB
Population:	Male and female term infants \geq 34 weeks gestation who have been diagnosed with virologically confirmed neonatal HSV disease via culture or polymerase chain reaction (PCR)
Sample Size:	6 - 10
Number of Sites:	1
Study Duration:	5 years
Subject Participation Duration:	up to 26 days
Description of Agent or Intervention:	Administration of valacyclovir for 2 to no more than 7 days in infants who have completed standard of care treatment course for neonatal HSV disease with high-dose parenteral acyclovir to obtain pharmacokinetic data. After 2 to no more than 7 days, the infant will be switched to the standard-of-care, oral acyclovir, to complete the standard 6 months of suppressive therapy.
Objectives:	
Primary:
 
• To define the pharmacokinetics of valacyclovir in neonates 2-12 weeks of age who are \geq 34 weeks gestation• To assess the safety of valacyclovir in treated infants 
Secondary:
 
• To assess the pharmacokinetics of high-dose parenteral acyclovir in neonates \geq 34 weeks gestation with virologically confirmed neonatal HSV disease who are receiving acyclovir as standard of care• To compare the pharmacokinetics of high-dose parenteral acyclovir to the pharmacokinetics of the proposed study dose of valacyclovir (20 mg/kg every 8 hours)

[figure not shown]
Outcome Measures	
Primary Endpoint:
 
 • Plasma pharmacokinetics parameters for valacyclovir AUC_8 • Cumulative incidence of Grade 3 or higher unsolicited adverse events, serious adverse events, or any adverse event that is not recovered / not resolved 
Secondary Endpoints:
 
 • Plasma pharmacokinetic parameters for parenteral acyclovir AUC_8 • Comparison of AUC_8 of 20 mg/kg IV acyclovir to the AUC_8 of 20 mg/kg PO valacyclovir
Description of Study Design:	
This is an open-label, single center, PK study to assess valacyclovir pharmacokinetics and pharmacodynamics in neonates and compare to the pharmacokinetics and pharmacodynamics of the standard of care treatment dose of intravenous acyclovir. Only those babies with virologically confirmed neonatal HSV disease will be enrolled in the study. The decision to initiate valacyclovir for 2 (up to 7) days will be made by a physician based on inclusion/exclusion criteria, and those who meet entry criteria will be eligible for the study. Those enrolled in the study will have daily random parenteral acyclovir PK levels drawn during the first week of treatment (drawn only at times of other lab draws). These infants will also have a pharmacokinetic sampling profile obtained on or after dose 22 and before dose 42 of intravenous acyclovir. The PK samples for the sampling profile will be collected just prior to the next dose of intravenous acyclovir (within 30 minutes prior to the start of the infusion), within 15 minutes of completion of the infusion, and 3-4 hours after infusion. Upon completion of the recommended treatment course duration with intravenous acyclovir determined by disease classification (SEM, CNS, or disseminated disease), the infant will be started on enteral valacyclovir 20 mg/kg every 8 hours.
 
On day 2 and no more than day 7 of valacyclovir 20 mg/kg every 8 hours, a pharmacokinetic sampling profile will be obtained. The PK samples will be collected just prior to the

enteral dose of valacyclovir hour 0 (8 hours after previous dose and immediately before next dose), 1-2 hours after dose, and 3-5 hours after dose.

Subjects with inadequate pharmacokinetic data for analysis (e.g., due to dropping out of the study before PK assessments are performed, or blood sampling obtained but is inadequate for analysis) may be replaced and will not count toward the total of 6 (and up to 10) subjects.

Estimated Time to Complete Enrollment: 4.5 years from enrollment of the first study subject

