2 BACKGROUND INFORMATION AND SCIENTIFIC RATIONALE

2.1 Background Information

Neonatal HSV is an uncommon disease that affects about 1500 infants yearly in the US (1-3) with recent studies indicating an increasing incidence over the last several years (4). Although uncommon, the disease can have devastating outcomes if not detected and treated early. The disease is divided into three classifications: skin, eye, and mouth (SEM), central nervous system (CNS), and disseminated. The classification is predictive of mortality and morbidity, with worse outcomes noted in the CNS and disseminated groups (5). SEM disease accounts for the majority of neonatal HSV disease cases (45%), followed by CNS disease (30%), and then disseminated disease (25%) (6).

Vidarabine was the first antiviral drug recommended for treatment of neonatal HSV disease in the 1970s. Although other antiviral agents were studied prior to vidarabine, they were not recommended for treatment of neonatal HSV disease as a result of their toxic side effects. Vidarabine was later replaced in the 1980s by acyclovir, an acyclic guanine analogue that inhibits viral replication by interfering with viral DNA polymerase (7-10). Although low dose acyclovir (30 mg/kg/day) was equally efficacious and demonstrated no reduction in mortality when compared to vidarabine (5, 6, 11), it was more favorable because of its less toxic profile and easier administration (6). A later study performed by the National Institute of Allergy and Infectious Diseases Collaborative Antiviral Study Group (CASG) evaluated intermediate dose acyclovir (45 mg/kg/day) and high dose acyclovir (60 mg/kg/day) to determine if outcome could be improved. High dose acyclovir demonstrated the greatest reduction in mortality rate from 14% in CNS disease and 54% in disseminated disease to 4% and 30% respectively (12). Thus, high dose acyclovir became the new standard of treatment for neonatal HSV disease, although the pharmacokinetics of high dose intravenous acyclovir dose were only assessed in two subjects (6, 12).

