Currently the standard of care requires that infants diagnosed with neonatal HSV disease are treated with high dose intravenous acyclovir for 14-21 days depending on classification of the disease (6, 13); infants with SEM disease are recommended to receive 14 days of intravenous acyclovir whereas infants with CNS and disseminated disease are recommended to receive at least 21 days of intravenous therapy. Those with CNS disease could potentially require longer than 21 days of therapy as duration of therapy is determined on clearance of viral DNA from the CSF via repeat lumbar puncture performed near the end of the 21 days of therapy(14). If the viral DNA is still detected, intravenous acyclovir is continued for an additional week and another lumbar puncture is performed. Infants remain hospitalized for the entire duration of treatment in order to closely monitor for the potential risk of renal toxicity, a common reversible side effect of intravenous acyclovir. Once the infant has completed the treatment

course of intravenous acyclovir, they are transitioned to oral acyclovir (300 mg/m²/dose three times a day) and discharged home to complete a total of 6 months of suppressive therapy to prevent further neurologic injury by subclinical viral replication (13, 15). Suppressive therapy has significantly improved neurologic outcome (higher neurodevelopmental scores) in those infants with CNS disease and decreased the number of skin recurrences when started immediately after completion of treatment with IV acyclovir (15, 16).

Although vast advancements have been made in the treatment of neonatal HSV disease to reduce mortality and morbidity, there remains a high emotional burden and demand on families as a result of guilt, lengthy hospitalizations, and frequent administration of medications for a prolonged period of time. There is also a large financial burden on healthcare systems; the estimated costs for treatment of neonatal HSV disease accounting for admission and 6 months of follow up in a cohort of 900 infants from 2009-2015 was more than 60 million dollars (4), which will continue to increase as the incidence of the disease increases. Preventing neonatal HSV disease would be ideal to reduce the emotional stress and demand on families and financial burden on healthcare systems, but until that time, other means of reducing these stressors should be evaluated.

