4 STUDY DESIGN

This study is an open-label, single-center, pharmacokinetic study of valacyclovir pharmacokinetics in male and female infants \geq 34 weeks gestation, \leq 42 days of age at initiation of intravenous acyclovir, and \geq 2000 g who have been diagnosed with virologically confirmed neonatal HSV disease via culture or polymerase chain reaction (PCR). Infants who meet the inclusion criteria will be eligible for the study, and informed consent will be obtained by the infant's parent(s) or legal guardian(s).

Subjects meeting enrollment criteria will be enrolled in this clinical trial. The total sample size will be 6 and up to 10 infants diagnosed with any of the 3 disease classifications of neonatal HSV disease. Following enrollment, infants during the first week of treatment with intravenous acyclovir as per standard of care will have daily random pharmacokinetic levels (population based pharmacokinetics) obtained at the same time of clinical blood draws (e.g. creatinine and/or CBC/diff), namely using remnant specimens. During the second week of treatment with IV acyclovir (between dose 22 and 42) infants will have one pharmacokinetic sampling profile obtained. The plasma specimens for the pharmacokinetic sampling profile will be drawn immediately prior to next dose (within 30 minutes prior to the start of infusion and 8 hours after previous dose) for an 8 hour trough, a post-infusion peak obtained within 15 minutes following completion of infusion, and 3-4 hours after infusion. Once these samples are obtained, the infant will complete the course of IV acyclovir per the standard of care guidelines.

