7.3 Study Follow-up

7.3.1. Period 1 (Treatment Day 1 through Treatment Day 7)

- Hematology labs

- WBC with differential will be recorded if being drawn for clinical reasons (any laboratory value obtained during the window will suffice, with an effort being made to capture the most abnormal value)
- Chemistry labs
 - Creatinine and alanine aminotransferase (ALT) values will be recorded if being drawn for clinical reasons
- Acyclovir pharmacokinetics
 - A single blood sample for PK determination will be obtained daily at random time intervals as able
 - Timepoints for pharmacokinetic draws will occur at random time intervals
 - Date and time of lab draw for PK specimen will be recorded
 - Date and time of last acyclovir infusion prior to PK lab draw will be recorded
 - Most recent patient weight, acyclovir dose received, and serum creatinine value will be recorded
 - Required amount of whole blood for plasma acyclovir determination at each timepoint is 200 μ L (0.2 mL)

Note: blood for PK assessments will be obtained at the time that a clinical blood draw is being performed, or through the indwelling intravenous catheter, so that no additional venipuncture procedures solely for study purposes will be required

7.3.2. Period 2 (Treatment Day 8 through Treatment Day 14 for SEM disease and Treatment Day 21 for CNS and disseminated disease)

- Hematology labs
 - WBC with differential will be recorded if being drawn for clinical reasons (any laboratory value obtained during the window will suffice, with an effort being made to capture the most abnormal value)
- Chemistry labs
 - Creatinine and alanine aminotransferase (ALT) values will be recorded if being drawn for clinical reasons
- Acyclovir pharmacokinetics
 - One acyclovir PK sampling profile will be performed after dose 22 and before dose 42
 - Acyclovir concentrations will be obtained at specified timepoints
 - Timepoints for pharmacokinetic draws: 0h (within 30 minutes prior to the start of the infusion of acyclovir), within 15 minutes after completion of the infusion, and 3-4 hours after infusion
 - Most recent patient weight, acyclovir dose received, and serum creatinine value will be recorded
 - Required amount of whole blood for plasma acyclovir determination at each timepoint is 200 μ L (0.2 mL)

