8.2.1.1. Acyclovir Pharmacokinetics

Assessment of acyclovir plasma concentrations will be conducted at the UAB Pharmacokinetic Laboratory. Acyclovir concentrations will be obtained on a daily basis at random time intervals during Period 1 (Treatment Day 1 through Treatment Day 7). One PK sampling profile will then be completed during Period 2 (between Treatment Day 8 and Treatment Day 14). Timepoints for pharmacokinetic draws for Period 2 are as follows: 0 hours (within 30 minutes prior to the start of the infusion), within 15 minutes after completion of the infusion, and 3-4 hours after infusion.

Pharmacokinetic specimens will also be obtained during Period 3 (Day 2 up to Day 7 of valacyclovir). The timepoints for the lab draws for Period 3 are as follows: 0 hours (just prior to the enteral dose of valacyclovir and approximately 8

hours after previous dose), 1-2 hours after dose, and 3-5 hours after dose. The required amount of whole blood for plasma acyclovir determination at each time point is 200 μ L (0.2 mL). Specimens will be processed to separate the plasma, and then will be transported to the UAB Pharmacokinetic Laboratory. Most recent patient weight, valacyclovir dose received, timing of dose, sample collection time, WBC, percentage neutrophils, ANC, ALT, and serum creatinine value will be recorded.

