APPENDIX A: SCHEDULE OF EVENTS (FOLLOWING ACQUISITION OF INFORMED CONSENT)

Blue font represents tests being obtained for clinical purposes

Gray boxes represent infants being treated for CNS or disseminated disease (these infants receive 21 days of therapy vs SEM disease patients who receive 14 days of therapy). No research labs will be obtained during this time.

	Treatment Day									
	Period 1							Period 2	Period 3	
	1	2	3	4	5	6	7	8 - 14	15 - 21	Day 2 (up to 7) of valacyclovir
Study Enrollment ^a	X									
Baseline demographics ^b	X									
Neonatal HSV disease Classification ^c	X									
Hematology labs ^d	X						X			
Chemistry labs ^e	X						X			
Acyclovir pharmacokinetics ^f	X ^g	X ^h								
Valacyclovir pharmacokinetics ⁱ										X ^j
IV acyclovir administration	←→									
Oral valacyclovir administration every 8 hours										↔
Total volume of blood required for study	0.2 mL	0.6 mL		0.6 mL						

- a) Participants can enroll in the study on or before treatment day 14, and therefore, data collected for each infant will be dependent on date of enrollment.
- b) Gestational age at delivery, postmenstrual age at delivery, date of birth, day of life at initiation of IV acyclovir therapy, gender, race, ethnicity, birth weight, weight at enrollment, length in centimeters at enrollment, acyclovir dose and frequency
- c) Treating physician's assessment of Skin-eye-mouth (SEM), central nervous system (CNS), or Disseminated neonatal HSV disease, based upon clinical assessments of skin lesions, skin viral studies, mucous membrane viral studies, CSF PCR, blood PCR, transaminitis, seizures, pneumonitis, coagulopathy, etc.
- d) WBC with differential, hemoglobin, platelet will be recorded if drawn for clinical purposes (any laboratory value obtained during the window will suffice, with an effort being made to capture the most abnormal value)

- e) All creatinine values will be recorded if drawn for clinical purposes. Any alanine aminotransferase (ALT) value obtained during the window will suffice, with an effort being made to capture the most abnormal value)
- f) A minimum of 200 μ L (0.2 mL) of whole blood is required for plasma PK analyses for acyclovir

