- g) A single plasma sample for PK determination will be obtained at each visit marked on the Schedule of Events. These samples will be obtained at random time intervals, but only at the time that a clinical blood draw is being performed, or through the indwelling intravenous catheter, so that no additional venipuncture solely for study purposes will be required; most recent weight, acyclovir dose received (date, time, and mg dose), and serum creatinine value will be recorded.
- h) Acyclovir concentrations will be obtained with one of the Study Assessment Doses between dose 22 and 42 (Study Day 8 through Study Day 14) at the following time points: 0h (within 30 minutes prior to the start of acyclovir infusion), within 15 minutes after completion of the infusion, and 3-4 hours after infusion.
- i) A minimum of 200 μ L (0.2 mL) of whole blood is required for plasma PK analyses for acyclovir
- j) Acyclovir concentrations will be obtained with one of the valacyclovir Study Assessment Doses (after dose 3 of valacyclovir) at the following time points: 0 hr (8 hours after previous dose), 1-2 hours after dose, and 3-5 hours after dose.

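### The IV acyclovir profile is held to about Treatment Days 8–14 in every disease class, which on a 21-day course adds an avoidable week (gap 9–20 days instead of 2–13) to the IV–oral AUC_8 comparison

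*Combined protocol and SAP*

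**What the plan says.** The IV window is stated in several places, without exception for disease class.

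- Protocol Summary, Description of Study Design: "These infants will also have a pharmacokinetic sampling profile obtained on or after dose 22 and before dose 42 of intravenous acyclovir".
- Section 4: "During the second week of treatment with IV acyclovir (between dose 22 and 42) infants will have one pharmacokinetic sampling profile obtained".
- Section 8.2.1.1 gives it in days: "One PK sampling profile will then be completed during Period 2 (between Treatment Day 8 and Treatment Day 14".
- Appendix A, note h, equates the two scales: "between dose 22 and 42 (Study Day 8 through Study Day 14".

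The IV course itself differs by class. SEM disease gets 14 days, while Section 2.1 says "infants with CNS and disseminated disease are recommended to receive at least 21 days of intravenous therapy", with the infant in hospital throughout. The heading of Section 7.3.2 accordingly runs "Period 2 (Treatment Day 8 through Treatment Day 14 for SEM disease and Treatment Day 21 for CNS and disseminated disease", yet the text below it keeps the dose 22 to 42 window. For the third week Appendix A says: "No research labs will be obtained during this time".

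Valacyclovir starts 8 hours after the last IV dose is completed (Section 4) and is profiled once, between its Day 2 and Day 7 (Section 7.3.3). Enrolment is open through Treatment Day 14 (Section 4). Section 11.4 compares mean AUC_8 for the two drugs in the same patients, using 95% confidence intervals around the means. It does not mention age or the interval between profiles.

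**The concern.** Comparability of oral valacyclovir with IV acyclovir is the primary hypothesis in Section 11.1 and a secondary endpoint in Section 3.2.2. Each infant supplies both profiles, which removes differences between infants. It does not remove change within an infant between the two profiles. Section 2.1 reports higher exposure in infants aged 1–2 months than in older ones and attributes it to lower clearance, so the protocol itself treats age as relevant in this range.

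IV always comes first, so a steady maturation effect would push every infant's ratio the same way, and enrolling more infants would not average it out. On a 21-day course the window adds a week to the interval although the infant is still in hospital on IV acyclovir. The documents give no reason for closing the window at dose 42 in that group. At stake is how cleanly the IV–oral ratio can be read as a route effect, and whether late enrollees on longer courses contribute a pair at all.

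**Working it through.** **Inputs.** IV dosing every 8 hours (Section 6.2), so three doses a day; IV profile at dose 22 up to but not including dose 42 (Protocol Summary); course length 14 or 21 days (Section 2.1, Appendix A); valacyclovir profile on its Day 2–7 (Section 7.3.3), after dose 3 (Appendix A, note j); case mix 45% SEM, 30% CNS, 25% disseminated (Section 2.1).

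**1. The plan's own mapping.** Treatment Day = dose/3, rounded up. Dose 22 gives 7.33, so Day 8. Doses 41 and 42 give 13.67 and 14, so Day 14. This reproduces Days 8–14 in Appendix A. With only one or two doses on calendar Day 1, dose 22 is still Day 8, and dose 41 is Day 15 or 14.

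**2. Gap in days.** For a course of L days, valacyclovir Day k is Treatment Day L + k. Minimum gap = (L + 2) − 14; maximum gap = (L + 7) − 8.

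| IV course | Valacyclovir profile, Treatment Days | Minimum gap | Maximum gap | Midpoint |
|---|---|---|---|---|
| 14 days | 16–21 | 16 − 14 = 2 | 21 − 8 = 13 | 7.5 |
| 21 days | 23–28 | 23 − 14 = 9 | 28 − 8 = 20 | 14.5 |

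**3. Check in 8-hour intervals.** This does not depend on how many doses fall on Day 1, and it ignores infusion length. Gap = ((N − k) + m)/3 days, with N = 42 or 63 IV doses, k = 22 to 41 and m = 4 to 21.

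- N = 42: (1 + 4)/3 = 1.7 to (20 + 21)/3 = 13.7 days.
- N = 63: (22 + 4)/3 = 8.7 to (41 + 21)/3 = 20.7 days.

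The difference is 7 days at each end.

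**4. With the profile on Days 15–21 of a 21-day course.** 23 − 21 = 2 to 28 − 15 = 13 days, the same as SEM.

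**5. How many infants.** 0.30 + 0.25 = 0.55. If the case mix holds among enrolled infants (assumption), 0.55 × 6 = 3.3 to 0.55 × 10 = 5.5 infants have the longer gap.

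**6. Possible size.** The documents give no rate of change in clearance. Assume clearance per kg rises by g per week. The valacyclovir/IV ratio is then multiplied by (1 + g)^(−gap/7).

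| Assumed g per week | 7.5-day gap | 14.5-day gap | Extra 7 days alone, f | Pooled: 0.45 + 0.55f |
|---|---|---|---|---|
| 2% | 0.979 | 0.960 | 0.980 | 0.99 |
| 5% | 0.949 | 0.904 | 0.952 | 0.97 |
| 10% | 0.903 | 0.821 | 0.909 | 0.95 |

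At the midpoint, 7.5 of the 14.5 days, about half, belong to the base gap that SEM infants also have.

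**7. Late enrolment.** Dose 42 falls on Day 14 or 15. An infant enrolled near Day 14 on a 21-day course can have no permitted IV profile while about seven days of IV remain.

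**The case against.** The strongest reply is that a single window is a coherent choice. IV acyclovir AUC_8 is a secondary endpoint in its own right, and a common treatment week puts that summary at the same point of therapy in every infant. A later window makes IV timing depend on disease class. That cost is real and must be reported. It is limited, because age at IV start may be anything up to 42 days, so a shared treatment week does not standardise age.

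Second, the effect may be small beside sampling error. If the within-infant SD of the log ratio is 0.20–0.30 (assumption), the 95% half-width t × SD/√n is 2.571 × 0.20/√6 = 0.21 to 2.571 × 0.30/√6 = 0.31 for six infants, and 2.262 × 0.20/√10 = 0.14 to 2.262 × 0.30/√10 = 0.21 for ten. A pooled shift of 1–5% is well inside that. This stands, and it argues for modest wording. It does not argue for keeping a week that costs nothing to remove.

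Third, Sections 2.1, 2.2 and 2.3.2 aim the results chiefly at SEM disease, whose gap is already 2–13 days. Also true, but all three classes are enrolled and no separate SEM analysis is planned.

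Three stronger readings are tempting and are not supported.

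- A reader might infer a known bias against valacyclovir. Section 2.1 compares broad age groups and says nothing about change over a week. It also calls renal toxicity a common, reversible effect of IV acyclovir, so even the direction is not established.
- A reader might add a 28-day course, with a gap of 30 − 14 = 16 to 35 − 8 = 27 days. That extension appears only in the background. Section 4 describes 14 to 21 days, and a 27-day gap exceeds the stated participation of up to 26 days.
- A reader might take the Study Day label in note h, with Study Assessment Day 1 set at enrolment in Section 4, as permission for later sampling. Section 4 fixes the window by Treatment Dose, and Appendix A bars the third week, so this is a labelling slip.

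**Conclusion.** The point holds as a design weakness of modest size. The documents establish one IV window for all classes, no research sampling on Days 15–21, gaps of 9–20 against 2–13 days, and the possible loss of the IV profile in late enrollees on 21-day courses. The extra week is avoidable: these infants remain hospitalised on IV, an indwelling catheter is expected (Section 2.3.1), and Section 7.3.2 already allows sampling through it.

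The figures of about 0.98/0.95/0.91 per affected infant and 0.99/0.97/0.95 pooled rest on an assumed 2/5/10% weekly rise in clearance. The pooled figures also assume that 55% of enrolled infants are on 21-day courses. Exclusions for imminent demise and creatinine could shift that share.

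It should not be inferred that a conclusion of the study would change: Section 11.4 is descriptive and sets no comparability margin. Nor is the valacyclovir AUC_8 endpoint affected. A later window would not make the comparison free of age, since a 2–13 day gap and the IV-first order remain.

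**What to change.** 1. For infants whose IV course runs past Day 14, allow, and where feasible prefer, the same three-sample IV profile on Treatment Days 15–21. Keep Days 8–14 as the fallback when a later profile is not expected to be feasible. Leave the SEM window unchanged. Amend the Appendix A note for that profile only, and carry the change through the Protocol Summary and Sections 4, 7.3.2 and 8.2.1.1.
2. In Section 11.4, make the IV–oral comparison a within-infant AUC_8 ratio or difference, with its confidence interval, in infants who have both profiles. Report age at each profile and the gap for each infant. Section 7.3.2 does not list the draw date, so make sure it is recorded.
3. Leave the replacement rule and the count of 6 to 10 as written.

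The cost is one amendment to the sampling window and its Appendix A note, and about two sentences in Section 11.4. Blood volume stays at 3 × 0.2 = 0.6 mL, and no infants are added. The downsides are that IV profile timing will vary by disease class and must be shown with the IV PK summary, and that waiting carries a small risk of losing the IV profile if IV ends early.
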